3.2 Exploratory Endpoints

- Change from Baseline (Day 0) in total mean Revised Amyotrophic Lateral Sclerosis Function Rating (ALSFRS-R) scores at Day 180 for Engensis compared to Placebo
- Change from Baseline (Day 0) in ALSFRS-R subscores for Fine and Gross Motor Functions (sum of scores for items 4 to 9) and for Bulbar Function (sum of scores for items 1 to 3) on Days 30, 60, 84, 120, 144, and 180 for Engensis compared to Placebo
- Changes in the slope of the total ALSFRS-R score over time for Engensis compared to Placebo
- Change from Baseline (Day 0) in muscle strength assessed bilaterally by Handheld Dynamometry (HHD) in muscles in the upper and lower extremities on Days 30, 60, 84, 120, 144, and 180 for Engensis compared to Placebo
- Change from Baseline (Day 0) in the Accurate Test of Limb Isometric Strength (ATLIS) where available at Days 30, 60, 84, 120, 144, and 180 for Engensis compared to Placebo
- Change from Baseline (Day 0) in Quality of Life (QoL) using the ALS Assessment Questionnaire (ALSAQ; with 40 items, ALSAQ-40) on Days 84 and 180 for Engensis compared to Placebo
- Patient Global Impression of Change (PGIC) and Clinical Global Impression of Change (CGIC) at Days 84 and 180 for Engensis compared to Placebo
- Change from Baseline (Day 0) in Slow Vital Capacity (SVC) on Days 30, 60, 84, 120, 144, and 180 for Engensis compared to Placebo
- Time to tracheostomy for Engensis compared to Placebo
- Time to all-cause mortality by Day 180 for Engensis compared to Placebo

QMD Ref: Worldwide-TMP-ST-005-7.0 Effective: 12Aug2019	Governing QMD: Worldwide-SOP-ST-001
Confidentiality Statement	

This document is the property of Worldwide Clinical Trials Inc. and may not be duplicated, copied, altered or removed from company without prior approval from Worldwide Quality Assurance or in compliance with Worldwide Standard Operating Procedures.

Worldwide Clinical Trials Controlled Quality Management Document		
 WORLDWIDE CLINICAL TRIALS	Sponsor:	Helixmith Co., Ltd.
	Protocol Number:	VMALS-002-2
STATISTICAL ANALYSIS PLAN VERSION 3.0		

- Change from Baseline (Day 0) in biomarkers for muscle atrophy in biopsies collected before and after injections for Engensis compared to Placebo

4 SAMPLE SIZE

A sample size of 18 Participants was chosen for safety assessments and preliminary evaluation of exploratory endpoints.

5 RANDOMIZATION

Participants are to be randomized on Day 0 as close as possible to the time of the first Study Injections. Randomization will be conducted via an electronic data capture system (EDC) randomization module in a 2:1 ratio for Participants to receive either Engensis or Placebo.

6 PLANNED ANALYSES

No statistical analysis plan (SAP) prepared in advance of the data can be absolutely definitive and the final Clinical Study Report (CSR) may contain additional tables or statistical tests if warranted by the data obtained. The justification for any such additional analyses will be fully documented in the final CSR.

6.1 Analysis Populations

6.1.1 Enrolled Population

Enrolled Population will be used for presenting data on Participant disposition, it will consist of all screened Participants.

6.1.2 ITT Population

The Intent to Treat (ITT) Population consists of all randomized participants. Participants will be grouped according to their planned treatment. Exploratory endpoints will be analyzed in the ITT Population.

6.1.3 Safety Analysis Population

Safety Analysis Population will be used to provide tables and listings for safety analysis.

The Safety Analysis Population will contain all Participants who are randomized and receive at least one Study Injection. Participants will be grouped according to their actual treatment received, not according to their randomization assignment (as randomized). Participants treated with any

QMD Ref: Worldwide-TMP-ST-005-7.0 Effective: 12Aug2019	Governing QMD: Worldwide-SOP-ST-001
Confidentiality Statement	

This document is the property of Worldwide Clinical Trials Inc. and may not be duplicated, copied, altered or removed from company without prior approval from Worldwide Quality Assurance or in compliance with Worldwide Standard Operating Procedures.

Worldwide Clinical Trials Controlled Quality Management Document			
 WORLDWIDE CLINICAL TRIALS	Sponsor:	Helixmith Co., Ltd.	
Protocol Number:			VMALS-002-2
STATISTICAL ANALYSIS PLAN VERSION 3.0			

Engensis dose will be grouped in the Engensis group; Participants treated without any Engensis will be grouped in the Placebo group.

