**FOOTNOTES FOR THE SCHEDULE OF ACTIVITIES**

**Note:** The Schedule of Activities includes activities during Screening and all Study Visits.

**Order of Assessments during Visits (if assessment is to be performed):** AEs/TEAEs, vital signs and weight, ALSFRS-R, HHD, ATLIS, pregnancy test, complete physical exam, SVC, ALSAQ-40, other questionnaires (PGIC and CGIC), blood sample collection for laboratory assessments, and muscle biopsy

- a Day 0 is the Baseline Visit
- b The Day 14 Visit will be scheduled 13-15 days after the Day 0 Visit, the Day 74 Visit will be scheduled 13-15 days after the Day 60 Visit, and the Day 134 Visit will be scheduled 13-15 days after the Day 120 Visit
- c Muscle biopsies will be collected as the last procedure of the Visit. It is collected predose on Day 0.
- d Day 84 muscle biopsy is optional.

**Abbreviations:** AEs = adverse events; AESI = adverse events of special interest; ALSFRS-R = Revised Amyotrophic Lateral Sclerosis Functional Rating Scale; ALSAQ-40 = Amyotrophic Lateral Sclerosis Assessment Questionnaire, 40 questions; ATLIS = accurate test of limb isometric strength; CGIC = Clinical Global Impression of Change; D = day; ET = early termination or withdrawal; HHD = Handheld Dynamometry; PGIC = Patient Global Impression of Change; SVC = Slow Vital Capacity; TEAEs = treatment-emergent adverse events; TESAEs = treatment-emergent serious adverse events

1. **Informed Consent** process is to be completed at Screening prior to conducting any study-specific procedures.
2. **Demographics and Baseline Characteristics** will include age, gender, race, and ethnicity and will be collected at Screening.
3. **Medical History and Familial Cancer History:** A medical history and familial cancer history will be obtained at Screening. The Investigator will confirm the diagnosis of ALS using the revised El Escorial / Airlie House diagnostic criteria. Participants will be confirmed as having clinically definite ALS, clinically probable ALS, or clinically probable laboratory-supported ALS  $\leq 4$  years.

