### **5.5. Participant Identification**

To maintain confidentiality, the name of the Participant should not be recorded on any study document other than the informed consent form. All Participants who sign the informed consent form will be assigned a unique identifier in the following format: XX-YYY where XX is the 2-digit Site number and YYY is the 3-digit sequential ID number starting with 001 for the first Participant consented at that Site. For example, the first Participant consented at Site 11 will be assigned 11-001. ID numbers for screen failures will not be reused. If a screen failure is later reconsented for rescreening, a new ID number will be assigned.

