6.3 Conventions

All data listings, summaries, figures and statistical analyses will be generated using SAS version 9.4 or higher¹ unless otherwise noted.

Summaries will be presented by treatment group. Treatment group labels will be displayed as follows:

Engensis (N=XX)	Placebo (N=XX)	Overall (N=XX)
--------------------	-------------------	-------------------

Listings will be sorted in the following order: treatment group, Participant, parameter, visit or cycle unless otherwise stated. All data will be listed.

Continuous variables will be summarized by the number of non-missing observations, mean, 95% confidence interval for mean, median, standard deviation, and minimum and maximum.

Categorical variables will be summarized by presenting the frequency and percent. Percentages will be based on the number of non-missing observations or the participant population unless otherwise specified. For each variable, all categories will be shown. Zero frequencies (but not the percent) within a category will be presented.

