6.14.1 Adverse Events

All study-related Adverse Events (AEs) will be collected starting after completion of the informed consent process at Screening to Day 0/randomization. Treatment-Emergent Adverse Events (TEAEs) and Treatment-Emergent Serious Adverse Events (TESAEs) will be collected after first injections on Day 0 through Day 180/End of Treatment or the last Study Visit up until the time that the Participant withdraws consent. All Serious Adverse Events (SAEs) will be collected from the completion of the informed consent process until Study Day 180 or the last Study Visit up until the time that the Participant withdraws consent. Any SAE occurring after consent and before the first injection on Day 0 should be recorded and reported only if associated with a protocol-specified procedure. Any AEs reported during Screening after completion of informed consent will be collected and recorded separately from TEAEs reported on Day 0 and through the end of the study.

Medical occurrences that begin before the start of study intervention and not related to required study procedures, but after obtaining informed consent will be recorded on the Medical History/Current Medical Conditions section of the eCRF and not as AEs.

Adverse events with relationship equal to “Possibly related”, “Probably related” and “Definitely related” will be considered as adverse events related to study medication. If an AE has missing relationship it is assumed to be related to the study drug for analysis purposes.

Adverse events with fatal outcome will be considered as fatal events. Maximum severity will be assumed for an AE with missing severity.

AEs will be coded using Medical Dictionary of Regulated Activities (MedDRA, version 23.0, or later) by System Organ Class (SOC) and preferred term (PT).

Adverse Event (AE) Definition

- An AE is any untoward medical occurrence in a patient or clinical study Participant, temporally associated with the use of study intervention, whether or not considered related to the study intervention.
- NOTE: An AE can therefore be any unfavorable and unintended sign (including an abnormal laboratory finding), symptom, or disease (new or exacerbated) temporally associated with the use of study intervention.

Treatment-Emergent Adverse Event (TEAE) Definition

QMD Ref: Worldwide-TMP-ST-005-7.0 Effective: 12Aug2019	Governing QMD: Worldwide-SOP-ST-001
Confidentiality Statement	

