The following tables will be presented:

- Summary of TEAE (Table 14.3.1.1)

QMD Ref: Worldwide-TMP-ST-005-7.0 Effective: 12Aug2019	Governing QMD: Worldwide-SOP-ST-001
Confidentiality Statement	

This document is the property of Worldwide Clinical Trials Inc. and may not be duplicated, copied, altered or removed from company without prior approval from Worldwide Quality Assurance or in compliance with Worldwide Standard Operating Procedures.

Worldwide Clinical Trials Controlled Quality Management Document			
 WORLDWIDE CLINICAL TRIALS	Sponsor:	Helixmith Co., Ltd.	
	Protocol Number:	VMALS-002-2	
STATISTICAL ANALYSIS PLAN VERSION 3.0			

- TEAEs organized by SOC and PT (Table 14.3.1.2)
- TESAEs organized by SOC and PT (Table 14.3.1.3)
- TEAEs organized by SOC and PT and Maximum Severity (Table 14.3.1.4)
- TEAEs organized by SOC and PT and Maximum Relationship (Table 14.3.1.5)
- TESAEs organized by SOC and PT and Maximum Severity (Table 14.3.1.6)
- TESAEs organized by SOC and PT and Maximum Relationship (Table 14.3.1.7)
- Incidence Injection site reactions by SOC and PT (Table 14.3.1.8)
- Incidence of clinically significant laboratory values (Table 14.3.1.9)
- AESIs organized by SOC and (Table 14.3.1.10)
- TEAEs leading to study discontinuation by SOC and PT (Table 14.3.1.11)
- TESAEs leading to study discontinuation by SOC and PT (Table 14.3.1.12)
- TEAEs leading to study drug withdrawal by SOC and PT (Table 14.3.1.13)
- TESAEs leading to study drug withdrawal by SOC and PT (Table 14.3.1.14)
- TEAEs related to study medication by SOC and PT (Table 14.3.1.15)
- TESAEs related to study medication by SOC and PT (Table 14.3.1.16)

The following listings will be provided:

- All AEs (Listing 16.2.7.1)
- AESIs (Listing 16.2.7.2)
- TESAEs (Listing 16.2.7.3)
- Injection Site Reactions (Listing 16.2.7.4)
- TEAEs leading to study discontinuation (Listing 16.2.7.5)
- TEAEs related to study medication (Listing 16.2.7.6)
- TESAEs leading to death (Listing 16.2.7.7)

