16.2.7.1	All Adverse Events – Safety Analysis Population	IP	
16.2.7.2	Adverse Events of Special Interest – Safety Analysis Population	IP	
16.2.7.3	Treatment-Emergent Serious Adverse Events – Safety Analysis Population	IP	
16.2.7.4	Injection Site Reactions – Safety Analysis Population	IP	
16.2.7.5	Treatment-Emergent Adverse Events leading to study discontinuation – Safety Analysis Population	IP	
16.2.7.6	Treatment-Emergent Adverse Events related to study medication – Safety Analysis Population	IP	
16.2.7.7	Treatment-Emergent Serious Adverse Events leading to death – Safety Analysis Population	IP	
16.2.8	Individual Laboratory Measurements		
16.2.8.1	Serum Chemistry – Safety Analysis Population	IP	
16.2.8.2	Hematology – Safety Analysis Population	IP	
16.2.8.3	Urine Pregnancy Test Results – Safety Analysis Population	IP	
16.2.8.4	Vital Signs – Safety Analysis Population	IP	
16.2.8.5	Electrocardiogram Results – Safety Analysis Population	IP	

QMD Ref: Worldwide-TMP-ST-005-7.0 Effective: 12Aug2019	Governing QMD: Worldwide-SOP-ST-001
Confidentiality Statement	

This document is the property of Worldwide Clinical Trials Inc. and may not be duplicated, copied, altered or removed from company without prior approval from Worldwide Quality Assurance or in compliance with Worldwide Standard Operating Procedures.

Worldwide Clinical Trials Controlled Quality Management Document			
 WORLDWIDE CLINICAL TRIALS	Sponsor:	Helixmith Co., Ltd.	
	Protocol Number:	VMALS-002-2	
STATISTICAL ANALYSIS PLAN VERSION 3.0			

Listing Number	Listing Title	Validation Method	Shell Number (if repeat)
16.2.8.6	Physical Examination Results – Safety Analysis Population	IP	
16.2.9	Exploratory Data		
16.2.9.1	Revised Amyotrophic Lateral Sclerosis Functional Rating Scale – ITT Population	IP	
16.2.9.2	Handheld Dynamometry – ITT Population	IP	
16.2.9.3	Accurate Test of Limb Isometric Strength – ITT Population	IP	
16.2.9.4	Amyotrophic Lateral Sclerosis Assessment Questionnaire, 40 questions – ITT Population	IP	
16.2.9.5	Clinical Global Impression of Change – ITT Population	IP	
16.2.9.6	Patient Global Impression of Change – ITT Population	IP	
16.2.9.7	Slow Vital Capacity – ITT Population	IP	
16.2.9.8	Time to Tracheostomy and Time to All-Cause Death – ITT Population	IP	
16.2.9.9	Muscle Atrophy – ITT Population	IP	
16.2.10	Exposure to Study Drug		
16.2.10.1	Exposure to Study Drug – Safety Analysis Population	IP	
16.2.10.2	Performed Injections – Safety Analysis Population	IP	

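### Adverse events in people who consent but are never injected appear in no AE table or listing, because every AE output is restricted to injected participants

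*SAP*

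**What the plan says.** **Reporting population.** SAP 6.1.3 states that "Safety Analysis Population will be used to provide tables and listings for safety analysis" and defines the set: "The Safety Analysis Population will contain all Participants who are randomized and receive at least one Study Injection". SAP Section 11 titles Listing 16.2.7.1 "All Adverse Events – Safety Analysis Population". SAP 6.1.1 reserves the Enrolled Population (everyone screened) for disposition. SAP 6.1.2 uses the ITT Population (everyone randomized) for exploratory endpoints.

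**Collection.** SAP 6.14.1 states that "All Serious Adverse Events (SAEs) will be collected from the completion of the informed consent process until Study Day 180", or the last visit before consent is withdrawn. It adds that an SAE before the first injection is recorded only if associated with a protocol procedure. Footnote 22 to the Protocol's Schedule of Activities runs AE recording from consent to the first injections.

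**Procedures before injection.** Footnote c to the same schedule says of the biopsy: "Muscle biopsies will be collected as the last procedure of the Visit. It is collected predose on Day 0". The Overall Design part of the Synopsis places that biopsy after randomization and before the first injections.

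**Rescreening.** Protocol 5.5: "If a screen failure is later reconsented for rescreening, a new ID number will be assigned".

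**The concern.** The trial's main objective is safety, and it performs an invasive procedure, a gastrocnemius biopsy, before any study drug is given. The window for collecting events opens at consent, but the gate for reporting them is the first injection. An event between the two is reported only if the person goes on to be injected.

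For most pre-injection events that is harmless. It matters when the event itself is why the injection did not happen. A complication bad enough to stop treatment drops out of the AE outputs, while a milder one that allows treatment stays in. The omission then depends on the consequence of the event. With 18 participants planned, one missing procedure-related event would be a visible hole in the account of harms. A reader of the study report could see that someone stopped for an adverse event and find no listing that describes it.

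**Working it through.** No arithmetic applies beyond a count. The plan gives no figure to reproduce on this point, so the check is which population each output uses and who falls outside it.

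**Step 1: count the outputs (SAP 6.14.1 and Section 11).**
- Tables 14.3.1.1 to 14.3.1.16: 16 of 16 on the Safety Analysis Population. (Table 14.3.1.9, on clinically significant laboratory values, sits in this block.)
- Listings 16.2.7.1 to 16.2.7.7: 7 of 7 on the Safety Analysis Population.
- Total: 16 + 7 = 23 of 23. On the ITT or Enrolled Population: 0.

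**Step 2: can someone have a recordable event and not be injected?** Protocol 4.1.1 puts the Day 0 biopsy last among the assessments before injection, and the Synopsis puts it after randomization. A participant can therefore be randomized, biopsied, have a complication and not be injected. That person belongs to the ITT and Enrolled Populations, neither of which has an AE output.

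**Step 3: follow the same Day 0 predose biopsy complication along two paths.**

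| | Then injected | Not injected |
|---|---|---|
| In the Safety Analysis Population | Yes | No |
| Listing 16.2.7.1 | Shown | Not shown |
| TEAE tables | Counted: the SAP 6.14.1 rule works by day and takes in the day of first dosing | Not counted: there is no day of first dosing |
| Listing 16.2.7.3 (TESAEs), if serious | Shown | Not shown |
| Disposition table and listing (SAP 6.4) | No entry for this event unless the person later stops because of it | At most, adverse event as primary reason for discontinuation |

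**Step 4: who else falls outside?**
- Screen failures with an event related to a screening procedure. They are never randomized.
- Rescreened people, for events in the first screening period. These sit under the old ID, which was never randomized. The SAP gives no rule linking old and new IDs, so that they fall outside Listing 16.2.7.1 is an inference from the two documents together.

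**Step 5: does another output describe the event?** Disposition gives a reason, not the event, its severity or its relationship. Heading 14.3.3 (narratives) names no population and at most would reach serious or otherwise significant events. The general convention in SAP 6.3, "All data will be listed", names no population and does not override the specific label on each listing.

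**The case against.** The strongest reply is that the group is small and nobody's safety depends on the listing.

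- **The group is narrow.** The biopsy comes after randomization, so screen failures undergo only the screening procedures in Protocol 8.1.1, such as blood draws, ECG, SVC and examination. Eligibility is adjudicated before randomization, and randomization falls on the day of the first injection. Under Protocol 8.5.1, pre-injection occurrences unrelated to procedures go to medical history (Protocol 8.2.2 is worded more broadly). This stands and limits the size of the point.
- **Oversight does not rely on this listing.** SAEs reach the sponsor within 24 hours, AEs and SAEs go to the regulator annually, and the DSMB reviews reported events under its own analysis plan. This also stands. The gap is in the study report, not in safety monitoring.

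Three stronger readings are tempting, and the documents do not support them.

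- *All events collected before injection go unreported.* Listing 16.2.7.1 covers all AEs, not only TEAEs, so it holds the pre-injection AEs and SAEs of everyone later injected. A Day 0 predose event in such a person even enters the TEAE tables.
- *Rescreened participants lose their pretreatment state.* Protocol 5.7 requires all screening assessments to be repeated, except viral screening done within 3 months. Baseline is the last value before the first injection (SAP 6.2.2). Only a first-screening AE can be lost.
- *SAP 6.3 contradicts the restriction.* That sentence is a general convention with no stated population. It neither closes the gap nor proves a conflict.

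None of these replies supplies an AE listing for a never-injected person.

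**Conclusion.** The point holds in a narrow form. AEs and procedure-related SAEs in people who consent but are never injected have no AE table or listing: 0 of the 23 outputs can show them. The most important case is the predose biopsy complication that prevents injection, because the same event in an injected participant would appear both in the listing and in the TEAE tables.

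The size of the gap cannot be computed. The documents give neither an actual nor an expected number of never-injected participants, and any percentage would rest on an invented count. It may be zero.

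TEAE and TESAE incidence among injected participants is unaffected, and so are the other primary endpoints. Restricting those tables to the Safety Analysis Population is right.

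The conclusion rests on two assumptions: that Section 11 population labels will be programmed as written, and that events between randomization and injection are captured as footnote 22 to the Schedule of Activities describes. This is a worthwhile, inexpensive correction to the reporting of harms, not a threat to the trial's main results.

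**What to change.** Amend SAP 6.1.1, 6.1.3, 6.14.1 and Section 11 as follows.

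- Run Listing 16.2.7.1 on the Enrolled Population, stated to mean everyone screened after consent.
- Add flags for randomized (yes/no), injected (yes/no) and pre-treatment SAE (yes/no).
- Link the old and new IDs of rescreened people, so that first-screening events can be read with the rest of the record.
- Say how never-injected people are displayed. SAP 6.3 sorts listings by treatment group, so a not-randomized category is needed, with planned arm for those randomized but not injected. Study day in SAP 6.2.3 counts from the first injection and is undefined for them; show the event date instead.
- Keep all TEAE and TESAE tables on the Safety Analysis Population.

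The cost is SAP and shell wording and a slightly longer listing. The data are already collected, and neither trial conduct nor any planned table changes.

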6.2 Derived Data

This section describes the derivations required for statistical analysis. Unless otherwise stated, variables derived in the source data will not be re-calculated.

